3. STUDY DESIGN

3.1. OVERVIEW

This multi-center, open-label, randomized study will enroll subjects with metastatic RCC of all histologies who have evidence of progression on or after the last regimen received and have also received at least 2 prior systemic regimens, 1 of which is an anti-VEGF agent (clear cell subjects). The study duration, up to the study's primary endpoint assessment, is approximately 24 months.

Non-clear cell RCC is a heterogeneous group of tumors typically not driven by von Hippel-Lindau (VHL) gene and sensitivity to anti-VEGF treatments differ from that shown in clear cell RCC. Hence, subjects with non-clear cell histology are only required to have progressed on or after only at least one anti-VEGF regimen. Subjects with non-clear cell histology must have ENPP3 positive immunohistochemical (IHC) staining at pre-screening. Positivity is defined as an IHC H-score ≥ 15 . Non-clear cell subjects whose tissue has an IHC H-score of ≥ 15 will qualify to screen for the study. Clear cell subjects are not required to be screened for ENPP3 to qualify for the study, but subjects must submit tissue during the study for retrospective target expression assessment by IHC.

Participants in this clinical investigation shall be referred to as "subjects". This study will enroll approximately 134 subjects. Within this total (i.e., 134), the number of subjects with non-clear cell histology is limited to 26 total.

Subjects will be randomized at 1:1 ratio to either AGS-16C3F or axitinib. Randomization will be stratified according to ECOG Performance Status (0 or 1), the number of prior systemic RCC regimens (2 or >2), and RCC histology (clear cell or non-clear cell). For stratification purpose:

- Non-clear cell subjects who have progressed after only one prior anti-VEGF regimen will be regarded the same as those clear cell subjects who have progressed after 2 prior systemic RCC regimens.
- Non-clear cell subjects who have progressed after >1 prior systemic RCC regimens will be regarded the same as those clear cell subjects who have progressed after >2 prior systemic RCC regimens.

AGS-16C3F will be administered at 1.8 mg/kg as a single 60-minute IV infusion once every 3 weeks. The dosage in mg will be calculated using the subject's actual body weight in kilograms at predose Cycle 1 Day 1 (C1D1). The same dose will be used throughout the study unless the subject's weight changes from baseline by $\geq 10\%$. In this case, the dose of AGE-16C3F will be administered based on the changed weight and this will become the new baseline weight for the purpose of planned dose recalculation and any further dosing decisions.

Therapy may be interrupted and/or the dose adjusted in case of toxicity. These subjects must also use 1% prednisolone acetate ophthalmic suspension (steroid eye drops) as prophylaxis, starting from Day -1 of each treatment cycle and extending through 7 days after the end of the cycle.

Axitinib is a commercial product and will be administered as defined in its product label. Axitinib will have a starting dose of 5 mg, twice daily continuously, by mouth. Axitinib dose may be adjusted during the study as needed as defined in the product label and local institutional guidelines, in doses ranging from 2 to 10 mg, twice daily continuously, by mouth.

Subjects will be eligible to continue receiving treatment on study until disease progression per RECIST v.1.1, unacceptable toxicity, investigator's decision, or study withdrawal. Subjects will also be discontinued from treatment if a significant non-compliance occurs (e.g., those that compromise study objectives or subject safety), or if a subject is lost to follow-up. The study may also be terminated by the Sponsor for any reason. Refer to Protocol Section 6 for details. All subjects will be required to have a Safety Follow-Up visit at least 28 days (+7 days) after the last dose.

Disease assessments will be performed every 8 weeks (± 7 days) counting from C1D1, without regard to any treatment delays. Bone scans will be performed every 12 weeks (± 7 days) counting from C1D1 (only subjects with bone disease at screening).

All subjects will be followed for survival approximately every 8 weeks from the Safety Follow-Up visit. This will be done by clinic visit or telephone, until death or study closure, whichever occurs first.

Those subjects who discontinued the study for reasons other than objective disease progression by RECIST v.1.1 will continue to have disease assessments every 8 weeks (± 7 days) counting from C1D1. This will continue until subject has radiologically confirmed progression, initiates a new therapy, or subject dies.

The primary efficacy endpoint is PFS based on investigator assessment utilizing RECIST v.1.1. Secondary efficacy endpoints include PFS per blinded central review per RECIST v.1.1, OS, and DCR, ORR, DOR (each of the 3 based on investigator radiographic review). Safety data and PK are also collected.

The study will have an Independent Data Monitoring Committee (IDMC) overseeing the study. The IDMC will conduct safety reviews at predetermined times during the study to make a recommendation for continuation of recruitment, protocol modification or study discontinuation for safety reasons.

The IDMC will minimally consist of a medically qualified individual, an ophthalmologist and a statistician. A separate IDMC Charter will specify the governance and conduct of the IDMC.

3.2. FLOW CHART AND SCHEDULE OF EVENTS

A flow chart of the study design and a Schedule of Events can be found in Protocol AGS-16C3F-15-3 Version 4.0 (Amendment 3), Section V.

3.3. CHANGES FROM PROTOCOL

Changes from the Protocol are cross-referenced in Table A.

Table A. Log of Changes from Protocol

Protocol Section	SAP Section and Change from Protocol	Rationale
Section 2.3.2, Secondary Objectives	Section 2.2, "Secondary Objectives", and throughout: The order of presentation of secondary endpoints changed from the protocol.	Sponsor request
Not Available	Section 2.3: Safety objectives that were implied but not stated in the protocol have been added.	Clarification
Section 4.4, Assignment and Allocation	Section 3.4: Some rephrasing has been done	Clarification
Section 5.1.1.3, Treatment Hiatus	Global: Treatment "hiatus" terminology has been changed to "treatment delay"	Sponsor request
Section 5.1.4.1, Treatment compliance of AGS-16C3F	Section 16: The overdose information has been removed per sponsor request and the compliance with steroid drops has been moved to Section 19.7 (other safety).	Sponsor request

Protocol Section	SAP Section and Change from Protocol	Rationale
Section 5.3.2, Medical History; Section 5.3.3 Diagnosis of the Target Disease, Severity, and Duration of Disease	Section 12: Ocular History has been added to the list of types of history for consistency with the eCRFs. All history has been reorganized to follow the eCRFs: (1) Disease History, (2) Prior Cancer Treatment History (Prior Cancer Systemic Therapy, Prior Cancer Radiotherapy), (3) Ocular History, (4) Medical History	Clarification
Section 7.2.2, Per Protocol Analysis Set	Section 5.2: Details regarding protocol deviations that will result in subject conclusion from the PPS have been added per sponsor communication.	Clarification
Section 7.3.4, Previous and Concomitant Medications	Section 14: Planned summaries of prior medications will not be produced	Sponsor request
Section 7.4, Analysis of Efficacy	Section 4.3, "Main Analysis" refers to the protocol-specified analyses to be conducted after primary database hardlock.	Clarification
Not available	Section 4.4: An End of Study analysis has been added	Sponsor request
Section 7.4.1.1, Primary Analysis	Section 17.1.2.1: Protocol-specified censoring rules are identified with respect to the regulatory recommendations and presented as Censoring Rules (Set 1).	Clarification
Section 7.4.1.2, Secondary Analysis	Section 17.1.4 has been titled "Sensitivity Analyses" to reflect the protocol content.	Clarification
Section 7.4.1.2, Secondary Analysis	Detail has been provided by adding Censoring Rules (Sets 2, 3, and 4) to Section 17.1.2.2, Section 17.1.2.3, and Section 17.1.2.4, respectively.	Clarification
Section 7.4.1.3, Subgroup Analysis	Section 17.4: Subgroup analyses in the PPS will not be done.	Sponsor request
Section 7.4.2, Analysis of Secondary Endpoints	Section 17.2.3.3, Section 17.2.3.4, Section 17.2.3.6: For all CMH analyses, the odds ratio will be reported instead of the relative risk for consistency between the estimates which are reported and the tests for treatment effect and homogeneity which are reported.	Sponsor request
Section 7.9, Handling of Missing Data, Outliers, Visit Windows, and Other Information:	Section 7.3: Text and cross-referenced SAP locations of different types of missing data were added.	Clarification
Not available	Section 13 follows the eCRF for Concomitant Procedures. A summary of concomitant procedures will be produced.	Consistency with collected data

Protocol Section	SAP Section and Change from Protocol	Rationale
Not available	Section 15, "Study Drug Exposure", was added. Summaries of AGS-16C3F exposure and axitinib exposure will be produced.	Regulatory requirement
Not available	Section 16.1, "Compliance with Disease Assessment Schedule", was added.	Recommended in regulatory guidance
Not available	Section 17.2.3.1, "Concordance of Disease Assessments by Independent Reviewers", was added.	Sponsor request.

3.4. ASSIGNMENT AND ALLOCATION TO TREATMENT

Randomization will be performed via Interactive Response Technology (IRT). After the subject has completed screening and been deemed eligible, the site staff will access the study's IRT system for subject randomization ≤5 days before C1D1. The IRT system will not allow randomization to occur if it has been more than 28 days since the main ICF has been signed. Specific procedures for randomization through the IRT are described in the study's IRT manual.

Subjects will be randomized at 1:1 ratio to either AGS-16C3F or axitinib. Randomization will be stratified according to ECOG Performance Status (0 or 1), RCC histology (clear cell or non-clear cell), and the number of prior systemic RCC regimens (2 for clear cell or 1 for non-clear cell, >2 for clear cell or >1 for non-clear cell).

The RCC histology categorization is defined as the following:

- Clear cell group:
 - Clear cell
 - Clear cell component
 - Mixed clear cell
- Non-clear cell group:
 - Papillary and everything else (e.g., chromophobe, collecting duct, renal medullary, etc., not so common but possible other RCC histologies)

Table B. Categories for Stratification of Prior Systemic RCC for Randomization Process

Prior Systemic RCC Regimen Stratum	Clear Cell Subjects	Non-Clear Cell Subjects
2	2 prior systemic RCC regimens	1 prior systemic RCC regimen
>2	>2 prior systemic RCC regimens	>1 prior systemic RCC regimens

Per protocol, subjects are expected to start study treatment ≤5 days after randomization.

3.5. SAMPLE SIZE JUSTIFICATION

For subjects with metastatic RCC who have progressed after at least 2 prior lines of therapy, a median PFS of 4 months is anticipated for the control agent. It is hypothesized that AGS-16C3F will improve median PFS in such subjects by 2 months (i.e., 4 vs 6 months). Under the assumption of exponential distribution of PFS, such an improvement corresponds to a hypothesized hazard ratio of 0.667. If this hypothesized hazard ratio is true, 110 PFS events provide 80% power to achieve a one-sided p-value of 0.1 or smaller. Such a result will be achieved when the observed hazard ratio is 0.783 or smaller; and the observed difference in median PFS is 1.1 months or larger (assuming observed median PFS for the control arm is 4 months). Assuming accrual of approximately 7 subjects per month for 18 months, 110 PFS events are projected 24 months after the date the first subject is randomized. Approximately 134 subjects may be enrolled to accommodate for up to 10% of subjects who may become lost to follow-up.

4. PLANNED ANALYSES

The following analyses will be performed for this study:

- Analyses for Independent Data Monitoring Committee (IDMC) meetings
- Main Analysis
- End of Study Analysis

A delivery date and an appropriate data cut-off date will be determined by the study team at least 8 weeks in advance of each planned analysis. Data used for planned analyses are expected to be as clean as possible prior to analysis and extracted with the agreement of the sponsor. The QuintilesIMS Data Management Interim Database Lock Plan for this study will provide detail.

4.1. INDEPENDENT DATA MONITORING COMMITTEE (IDMC)

The study will have an Independent Data-Monitoring Committee (IDMC) overseeing the study. The IDMC will conduct safety reviews on a periodic basis during the trial and will make a recommendation for continuation of recruitment, protocol modification or study discontinuation for safety reasons.

It is anticipated that the first IDMC data review meetings will be scheduled to occur via teleconference after the first 25 subjects have been enrolled and participated in study for at least 100 days; subsequent reviews will occur every 6 months. The data which are presented for review will be cumulative, and are expected to be as clean as possible prior to each data snapshot.

The outputs for the safety data review will be a subset of the outputs which are planned for the main analysis. A separate DMC SAP will not be written. A list of the outputs to be generated for each safety review meeting will be provided by Quintiles as a separate document.

Results will have limited distribution and will be disseminated only to the IDMC and to the parties within Agensys and Quintiles who are specified in the study Unblinding Plan. This is to avoid raising significant concerns about introducing potential bias into the conduct of the study or into subsequent decisions regarding the conduct of the study.

The full procedures for IDMC data review will be described in a separate IDMC charter.

4.2. MAIN ANALYSIS

The purpose of the Main Analysis is to establish proof of concept for AGS-16C3F in the treatment of RCC, based on efficacy, safety and PK data; and to support preparation of a Clinical Study Report (CSR).

The Main Analysis is planned after approximately 110 PFS events are observed. The data cut-off date for the Main Analysis will be determined based on the primary efficacy endpoint of PFS under the Censoring Rules (Set 1). Data from visits and assessments that occurred prior to or on the cut-off date are expected to be complete and all critical fields are expected to be clean. Data that occurred after the cut-off date yet entered in the EDC prior to data extraction will be excluded from the main analysis.

The planned analyses identified in this SAP will be performed by Quintiles Biostatistics following sponsor authorization of the SAP, sponsor authorization of the analysis sets, and sponsor permission to lock the database. The study Unblinding Plan provides more detail.

PK parameter estimation will be performed by the Agensys pharmacokineticist and is outside the scope of this SAP. However, Quintiles will report the PK concentration results and PK parameter estimates for the Main Analysis as described in this SAP.

4.3. END OF STUDY ANALYSIS

An End of Study Analysis will be performed at the discretion of the sponsor when any one of the following conditions occurs:

- The IDMC recommends stopping the study
- AGS-16C3F has been either approved or rejected by every country in which subjects were enrolled in the study
- Every randomized subject has met one of the following conditions: (1) the subject has discontinued from the study, or (2) the subject has been followed for a minimum of 12 months after discontinuing treatment, or (3) the subject has been followed for 12 additional months after the planned Main Analysis was performed.

The End of Study Analysis is expected to include safety analyses of AEs and efficacy analyses of the PFS and OS.

5. ANALYSIS SETS

The sponsor will make decisions about subject exclusions from analyses and authorize/approve the analysis set membership prior to each reporting event. Membership in all analysis sets will be determined prior to the Main Analysis, based on all data available at that time. Analysis sets will be updated if appropriate at the time of the End of Study Analysis, and any changes between the Main Analysis and the End of Study Analysis sets will be documented.

5.1. FULL ANALYSIS SET [FAS]

In accordance with the intention-to-treat (ITT) principle, the full analysis set (FAS) will consist of all subjects who are randomized to study drug. This will be the primary analysis set for efficacy analyses. The subjects will be grouped for purposes of the analysis according to the treatment assigned by the randomization, regardless of whether the subject receives the correct drug assignment.

5.2. PER PROTOCOL ANALYSIS SET [PPS]

The per-protocol analysis set (PPS) will consist of all subjects in the FAS who did not experience protocol deviations that might affect the efficacy endpoints. Important protocol deviations that might affect efficacy are defined separately for each version of the protocol, as the inclusion/exclusion numbering may change between versions. Specifically, subjects are expected to be excluded from the PPS due to the following reasons:

- PD1 - Did not meet the inclusion/exclusion criteria that are prognostic of the efficacy endpoints; i.e., one or more of:
 - Original Protocol, Amendment 1, Amendment 2, or Amendment 3: Inclusion Criteria 3, 4, 5, 7, 9, 10 or Exclusion Criteria 1, 2, 3, 4, 5, 6, 8, 9, 10, 11, 12, 14.
- PD2 Developed withdrawal criteria during the study and was not withdrawn.
- PD3 - Received wrong treatment or incorrect dose
 - Did not receive treatment
 - Not treated as assigned (i.e., received the wrong drug)
- PD4 – Received excluded concomitant treatment
 - Prohibited concomitant medication [see SAP Appendix 3]
 - Prohibited non-drug therapy [see SAP Appendix 3]

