### **2.2.3 Number of Subjects**

Participants in this clinical investigation shall be referred to as “subjects”. This study will enroll approximately 134 subjects total. Within this total (i.e., 134), the number of subjects with non-clear cell histology is limited to 26 total.

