##### **3.1.1 Prescreening**

Subjects with RCC of non-clear cell histology must sign the prescreening ICF and be prescreened for ENPP3 expression prior to undergoing screening procedures for the main study. Refer to Section 5.2.2 for details.

Clear cell histology subjects are not required to be prescreened for target expression to qualify for the study but must provide tissue during the study for ENPP3 determination by IHC.

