#### **3.2 Inclusion Criteria**

1. Is at least 18 years of age
2. Histologically confirmed diagnosis of RCC
  - a. Non-clear subjects must be ENPP3 positive, defined as IHC H-score  $\geq 15$
3. Has evidence of progression on or after the last regimen received:

- a. Clear cell subject: must have received at least 2 prior systemic regimens, one of which is an anti-VEGF agent.
  - b. Non-clear cell subject: must have received at least one prior anti-VEGF regimen
4. Has measurable disease according to Response Criteria for Solid Tumors (RECIST v.1.1)
5. Has ECOG Performance Status of 0 or 1
6. Has archive tumor tissue from primary tumor or metastatic site (excluding bone), for which the source and availability have been confirmed.
  - a. If no archive tissue is available, the subject may elect to have a biopsy performed to obtain tissue.
7. Has adequate organ function including:
  - a. Hematopoietic function as follows:
    - i. Absolute neutrophil count (ANC)  $\geq 1.5 \times 10^9/L$
    - ii. Platelet count  $\geq 100 \times 10^9/L$
    - iii. Hemoglobin  $\geq 9$  g/dL (transfusions are allowed)
  - b. Renal Function as follows:
    - i. Creatinine  $\leq 1.5 \times$  ULN, or calculated GFR  $> 40$  mL/min (Cockcroft-Gault) if creatinine  $> 1.5 \times$  ULN
  - c. Hepatic function, as follows:
    - i. Aspartate aminotransferase (AST) and Alanine aminotransferase (ALT)  $\leq 2.5 \times$  ULN or  $\leq 5 \times$  ULN if known liver metastases
    - ii. Total bilirubin  $\leq 1.5 \times$  ULN
8. Prothrombin time (PT) and activated partial thromboplastin time (aPTT) levels  $\leq 1.5 \times$  ULN. If institution does not report PT value, the INR must be  $\leq$  ULN
  - a. If subject is receiving Coumadin (warfarin), a stable international normalization ratio (INR) of 2-3 is required.
9. No clinical symptoms of hypothyroidism
10. Urine Protein to Creatinine Ratio (uPCR)  $< 2.0$ 
  - a. If uPCR  $\geq 2.0$  then a 24-hour urine collection can be performed to qualify. If this is performed to qualify, the protein result must be  $< 2$  g per 24 hours.
11. Female subject must either:
  - a. Be of non-childbearing potential:
    - i. post-menopausal (defined as at least 1 year without any menses) prior to Screening, or
    - ii. documented surgically sterile

- b. Or, if of childbearing potential,
  - i. Agree not to try to become pregnant during the study and for 6 months after the final study drug administration

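### The per-protocol exclusion list in SAP 5.2 omits Inclusion Criterion 2 (confirmed RCC, and ENPP3 positivity for non-clear cell subjects)

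*SAP*

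**What the plan says.** SAP 5.2 defines the PPS as "all subjects in the FAS who did not experience protocol deviations that might affect the efficacy endpoints". It then gives four deviation categories expected to lead to exclusion. The first, PD1, is introduced as "Did not meet the inclusion/exclusion criteria that are prognostic of the efficacy endpoints; i.e., one or more of", followed by a single list for the original protocol through Amendment 3: "Inclusion Criteria 3, 4, 5, 7, 9, 10" on the inclusion side, and twelve exclusion criteria (1–6, 8–12 and 14).

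In Protocol 3.2, Inclusion 2 is "Histologically confirmed diagnosis of RCC". Its sub-item 2a adds "Non-clear subjects must be ENPP3 positive, defined as IHC H-score" of 15 or more. Protocol 3.1.1 confines the target requirement to one histology group: "Clear cell histology subjects are not required to be prescreened for target expression to qualify for the study". Protocol 2.2.3 caps that group: "the number of subjects with non-clear cell histology is limited to 26 total", out of about 134.

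Protocol 7.2.2 leaves the PPS exclusion criteria to the SAP. Protocol 7.7 defines its own PD1 as failure of any entry criterion. SAP Table A records that the detail was added following sponsor communication, but gives no reason for omitting Inclusion 2.

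**The concern.** The list is narrower than the principle it is meant to carry out. Whether a subject has RCC plainly bears on PFS. For a conjugate directed at ENPP3, failing the target requirement is at least a deviation that might influence efficacy. Yet the list acts on hypothyroid symptoms, urine protein and ocular conditions (Exclusion 5) and is silent on disease and target.

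What is at stake is how informative the PPS is. SAP 17.1.4.1 uses it to test whether the primary PFS result is robust to major deviations, and SAP 17.2.3 repeats every secondary efficacy analysis in it. If an Inclusion 2 violator exists and stays in both sets, comparing FAS with PPS cannot show that subject's influence. Removing the subject would then need a decision outside the list, in an open-label trial.

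**Working it through.** **1. The plan's own figure, for scale.** Inputs from SAP 3.5: HR 0.667, one-sided alpha 0.1, power 80%, and 1:1 allocation.

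- Events = 4(1.2816 + 0.8416)² / (ln 0.667)² = 18.03 / 0.1640 = 110, as stated.
- Critical HR = exp(−1.2816 × 2/√110) = 0.783, as stated.
- Median difference = 4/0.783 − 4 = 1.1 months, as stated.

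None of these depends on the PPS, so adding a criterion to PD1 changes none of them.

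**2. What the list leaves out.** Compared with the sixteen inclusion and sixteen exclusion criteria in Protocol 3.2 and 3.3:

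- Inclusion criteria not listed: 1 (age), 2 (RCC and ENPP3), 6 (tissue), 8 (coagulation), 11–15 (pregnancy, contraception, breastfeeding, donation) and 16 (consent).
- Exclusion criteria not listed: 7 (sensitivity to ingredients), 13 (pregnancy or lactation), 15 (unwilling or unable to comply) and 16 (disorder affecting consent or compliance).

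Inclusion 2 is the only omitted criterion that defines the disease or the target.

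**3. Tracing a violator.** Take a non-clear cell subject with an H-score below 15 who has progressed after anti-VEGF therapy, has measurable disease, ECOG 0 or 1 and adequate organ function, and meets every other criterion.

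- PD1: Inclusion 3b, 4, 5, 7, 9 and 10 are met and no listed exclusion applies, so it is not triggered.
- PD2 (should have been withdrawn but was not): does not name this failure.
- PD3 (untreated or wrong drug): not triggered.
- PD4 (prohibited treatment): not triggered.

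The subject stays in the PPS under the listed rules.

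**4. Reach.** The ENPP3 part can apply to at most 26/134 = 19.4% of subjects. The other 134 − 26 = 108 or more have no ENPP3 entry requirement.

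**5. Illustration of dilution.** Assumptions, none from the documents: k violators have HR 1, the rest have HR 2/3, log hazard ratios average in proportion, and events stay at 110. Then HR = exp[(1 − k/134) ln(2/3)] and power = Φ(√110 × |ln HR| / 2 − 1.2816).

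| k | HR | Power |
|---|---|---|
| 0 | 0.667 | 80.1% |
| 1 | 0.669 | 79.6% |
| 5 | 0.677 | 77.8% |
| 26 | 0.721 | 66.7% |

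The last row is a ceiling at which every non-clear cell subject fails the rule. It is not a plausible case.

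**The case against.** The strongest reply is that the list need not decide the matter. SAP 5.2 words the exclusions as expected ones, SAP 5 gives membership decisions to the sponsor before each reporting event, and Protocol 7 and 7.2 provide for Classification Specifications and a classification meeting. This softens the point. PD1 itself still reads as closed, and exclusion on an unlisted criterion would be an ad hoc choice in an open-label trial.

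There are partial backstops. Under Protocol 6.1 a significant deviation that compromises study objectives is a reason to stop treatment, so a subject kept on drug despite one could meet PD2; a subject who was stopped would not. Inclusion 3, which is listed, is written separately for clear cell and non-clear cell subjects, so a subject without RCC arguably satisfies neither half. That weakens the wrong-tumour case but leaves the ENPP3 case untouched. It could also be said that PD1 speaks of prognostic criteria and that the documents do not show ENPP3 to be prognostic. But the governing sentence asks only whether a deviation might affect efficacy.

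Violators should also be rare. Non-clear cell subjects need a qualifying score from the sponsor-designated laboratory before they may screen (Protocol 5.2.1 and 5.2.2), and an eligibility worksheet is submitted for review (Protocol 5.2.3).

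A reader might infer three stronger things that the documents do not support.

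- **That the PPS is meant to be a target-positive set.** It is not. Clear cell subjects enter at any ENPP3 level. Protocol 1.1.3 reports high expression in about 90% of clear cell tumours. If that rate held here (an assumption, and high expression is not the same threshold as an H-score of 15), about 108 × 0.10 = 11 clear cell subjects would lack it and stay in the PPS, with or without the fix.
- **That a few violators can be predicted.** The documents give no failure rate and plan no re-read of scores.
- **That missing target is the deviation most likely to dilute the effect.** Nothing in the documents shows this.

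**Conclusion.** The omission is real and sits uneasily with the SAP's own definition of the PPS. It is a minor defect in a sensitivity set. It matters only if at least one subject is randomized despite failing Inclusion 2. The ENPP3 part is bounded by 26 of 134, and zero violators is entirely possible. The FAS analysis, the 110 events and the significance level are untouched.

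The conclusion rests on version 6.0 criterion numbering, the only one available. The listed numbers fit it (progression, measurable disease, ECOG, organ function, hypothyroidism, urine protein), but SAP 5.2 itself warns that numbering may differ between versions. The list stops at Amendment 3 while the protocol now carries Amendment 5. A reader might take that as a further gap, but the documents do not show that anyone was enrolled under a later version, and the substantial changes listed for Amendment 5 do not alter eligibility.

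**What to change.** Add Inclusion Criterion 2, including 2a, to the PD1 list in SAP 5.2, or state why it is left out. Before doing so, confirm which number the criterion carries in each protocol version that the list covers. Extend the list beyond Amendment 3 only if subjects were enrolled under a later version.

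The cost is one entry in a list plus a numbering check. No sample size, primary analysis or data collection changes. If the analyses have already been run, Protocol 7 requires departures from the SAP to be justified in the clinical study report. A statement there of how many randomized subjects failed Inclusion 2, even if none, would settle the point.
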